Health and Care Services has recommended further development of the GTT method to more accurately measure AEs with automatic identifications and more disease specific models (3,4). Patient Reported Outcomes (PRO) and Outcomes Measures (PROM) have shown to better describe the patients' symptoms compared to reporting from health care professionals (5). A recent systematic review of 22 studies including PROMs in daily cancer care found that follow-up by PROMs had a positive effect on survival, symptoms, health related quality of life and patient satisfaction (6). Consequently, PROMs are seen as the preferred method and gold standard to gather information from the patients in studies and real-life, as they often give a more convincing picture of the patients' wellbeing and side effects from interventions and treatments (5). Studies have demonstrated that electronic PROs (e-PROs) as follow-up for cancer patients under chemotherapy treatment can reduce acute admission to hospitals, improve quality of life (QoL) and prolong overall survival with up to 7 months compared to follow-up by standard care (5,6). There are national recommendations for research to; a) increase quality and efficacy in health care; b) promote personalised, patient centred health; c) improve prediction and diagnostics; d) increase use of e-health; and e) increase innovation in clinical practice (7). To our knowledge there are no studies published on how e-PRO follow up affects rates of severe adverse events, QoL and survival of cancer patients receiving immunotherapy treatment. In our research we will study immunotherapy related AEs(irAEs) in real time and investigate if ePRO follow-up can reduce severe irAEs, influence QoL and perhaps also increase survival compared to standard follow-up of cancer patients.

In 2013, Nordland Hospital Trust (NLSH) in collaboration with SAS Institute (SAS) developed a modified half automated version of the GTT method, called Nordic Clinical Analytics Framework (NCAF). Here machine learning (ML)-methods make it possible to find records with positive triggers which then are manually reviewed to verify if the triggers represent a true AE. Previous research on this half-automated technology have shown that it can efficiently replace manual identification, saves time and resources identifying AEs (8). From 2017 the NCAF method has been used by all hospital trusts in Northern Norway, however it has some drawbacks. Firstly, technology to fully automate identification of AEs is not yet developed. Secondly, NCAF lacks cancer-specific triggers to identify AEs related to systemic anticancer treatment such as chemotherapy, immunotherapy and other targets therapies. This makes it difficult to both identify, compare, and monitor AEs over time for cancer patients (1,9-12). To develop an automated identification of AEs we need to identify relevant triggers, before incorporating them into the NCAF technology. Recently a few studies have validated cancer-specific triggers, nevertheless, none of these validated oncology trigger tools uses automated identification of AEs (9-12). Furthermore, validated triggers to identify AEs related to modern anticancer treatments such as immunotherapy do not exist today. Immunotherapy introduces a different type of autoimmune AEs that can affect every organ system and causes 15 % severe AEs. To prevent development of severe irAEs it is important with early detection, since they can be reversed

[figure not shown]

Figure 1: E-PRO follow-up with Kaiku Health

As the first hospital in Norway, the Cancer Department at NLSH implemented ePRO follow-up as standard of care for all patients receiving immunotherapy from June 2021 by using Kaiku Health. The immunotherapy module is based upon reported irAEs in clinical trials of immunotherapy (15-17). Kaiku health is a web-based program for smartphones, I-pads and home computers, and by using ML algorithms the software screen, grade and alert for potential harm. Based on received treatment each patient gets a personalised follow-up symptom- and QoL-questionnaire (the European Organisation of Research and Treatment of Cancer, EORTC, recommended QoL-module called QLQ C-30(18)) sent out regularly. Filled-out questionnaires are submitted digitally to the Cancer Department which is able to see in real-time the patient's status, and directly identify possible symptoms. This makes it easier to respond immediately to potentially serious irAEs and prevent further impairment of the patient. At the same time as the health care professionals are alerted, the patient gets information on his/her own device about how they should react and what to do, and how their symptoms have evolved over time. Figure 1 illustrates how ePRO follow-up with Kaiku Health works in clinical practice.

From analysing the current methods and technologies used to monitor AEs caused by anticancer treatment, we intend in work package (WP) 1 to develop and validate a fully automated cancer-specific trigger tool to identify irAEs occurring in both hospitalised and outpatient clinical practice, called NCAF Oncology. In WP 2 we will study how the NCAF Oncology works in clinical care, and compare the incidence and development of irAEs between cancer patients followed by ePRO compared to standard of care. In WP3 we investigate how QoL in cancer patients evolves under immunotherapy treatment with follow-up by ePRO, and also compare overall survival between standard and ePRO follow-up.

with timely intervention (13,14). Thirdly, NCAF only analyses hospitalised patients while most cancer patients receive ambulatory treatment, so monitoring AEs in an outpatient setting is essential to map the full extent of AEs.

1.1 Expected benefits

By developing novel technology relevant in clinical practice our ambitions are to develop and validate the first fully automated NCAF Oncology method to monitor irAEs specific to modern immunotherapy anticancer treatment both in hospitalised and outpatient settings, with the future purpose to measure and mitigate irAEs with use of less resources. The key **academic impact** is validated technological methods to monitor irAEs from systemic anticancer treatment that can be directly implemented in everyday clinical practice. Development of a fully automated NCAF Oncology can be used to develop similar technological methods to identify AEs in other medical specialties. Improvement of the NCAF allows further research on prospective warning signals and clinical support integrated in the electronic health record (EHR) to mitigate other AEs in cancer care. The use of ePROs and QoL-score provides personalized follow-up to the patients. It also gives healthcare professionals the opportunity to focus on the patient`s perspective at the same time as they can mitigate and prevent harm before it results in a severe irAE. Importantly, the patients are proactive in their own patient journey with more knowledge about their own symptoms and how to react on them. This encourages empowerment and safety to the patient and their family, and has proved to reduce symptoms such as pain, depression and fatigue and increase patient`s QoL (6). It could also decrease the need for emergency admissions or unplanned visits/ phone calls at the outpatient clinic (5,6,15), which can be a burden to the patient, their family and the healthcare system. Knowledge about real time follow up and irAEs can be clinically relevant to better inform patients before starting new treatments. It may also provide information about when to end potentially harmful and high cost treatment, as alerted symptoms and/or decreasing QoL can signal toxicity or progressive disease (5,6,16,17).

2 The student`s contributions into the project

The PhD student will be responsible for data collection, analysis and writing of all articles in WP1-3. For detailed plan of candidate`s contributions see assigned tasks in project plan, section 5 *Project plan and overview of activities*.

3 Overall aim and hypotheses

3.1 Aim and objectives

The overall **aim** is to enhance patient safety and personalised follow-up for cancer patients by developing and implementing new technology to monitor AEs caused by immunotherapy as a systemic anticancer treatment in everyday clinical practice. To achieve this, we will focus on:

- 1) Improve the NCAF-methodology to include specific oncology triggers for more precise and accurate automated identification of irAEs.
- 2) Involving cancer patients more in their treatment by developing and implementing personalised e-PRO follow-up to reduce irAEs and improve patient outcomes in clinical practice.

To reach the main goal, we need to address the following **objectives (O)**:

O1: Develop and validate specific oncology triggers with high sensitivity and specificity for fully automated identification of irAEs.

O2: Implement personalised ePRO immunotherapy follow-up for cancer patients and investigate the incidence and severity of irAEs.

O3: Implement personalised ePRO immunotherapy follow-up and investigate Health Related QoL (HRQoL) and overall survival compared to standard of care.

3.2 Hypotheses and research questions

We have identified the following hypotheses (H):

H1: We predict that the new developed NCAF Oncology can identify rates, type and severity of irAEs with high sensitivity and of relevance in clinical practice.

H2: By implementing ePRO as standard follow-up for cancer patients we predict that we can reduce the incidence of severe irAEs.

H3: By implementing ePRO as standard follow-up for cancer patients we predict that we can increase HRQoL and overall survival.

4 Materials and methods

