4.2 Study design and methodology

A retrospective quantitative approach will be used to develop and validate new technology and methods since there is a need to control and check the outcomes, before we use an ambi-directional cohort study design to see how the new technology and methods perform in clinical practice on real

world data (20). The study is a multicentre study carried out at the Department of Oncology at NLSH in collaboration with The University Hospital of North Norway (UNN) and Helgeland Hospital Trust (HSYK).

The main inclusion criteria are above 18 years of age, cancer diagnosis as primary or secondary diagnosis according to the ICD-10 classification and receiving immunotherapy as systemic anticancer treatment reported with ATC codes for medications. Patient data will be collected from the hospitals shared EHR. Extracted information from patient records will be anonymised and stored within an encrypted environment at NLSH with restricted access only to certified study personnel, and kept for ten years. No data will be transferred outside the EEA.

The project is operationalised into three work packages (WPs) where cancer patients from all three hospital trusts will be included in one large cohort in WP1. In WP2 and 3 a prospective cohort will be compared to a retrospective cohort from WP1. Figure 2 under is an overview of the three WPs.

[figure not shown]

Figure 2: Overview of the three WPs

The specific methods, tasks (T), description of activities and the outcome deliverables (D) used for each WP are divided and specified in the tables below.

WP1: Automated identification of irAEs in cancer care
Target: WP1 is based on H1, with the aim to reach O1.
Method: Multicentre retrospective cohort study
Description of activities: 600 cancer patients treated with immunotherapy from 2021-2022 will be included and prepared for analytics in a separate technological environment. The use of corticosteroids, Infliximab or

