T2.3 Comparing rates, types, severity of irAEs between ePRO follow up and standard of care	D2.3 Statistical analyses of differences between groups
T2.4 Write article about findings	D2.4 Published article

WP3: Influence on QoL and OS of ePRO follow-up as standard of care

Target: WP3 is based on H3 with the aim to reach O3

Method: An ambi- directional multicentre cohort study	
Description of activities: 300 patients receiving immunotherapy and followed by ePRO during 2024-2025 from NLSH and HSYK will be included in a prospective arm. These will be compared to a retrospective cohort of 600 patients from WP1 including patients from UNN and HSYK with standard follow-up who received immunotherapy during the years 2020-2023, and matched on cancer diagnosis. HRQoL will be measured using EORTC QLQ-C30 version 3.0(18,19) included in the ePRO module. Overall survival will be compared using Kaplan Meier analysis.	
Tasks	Deliverables
T3.1 Data collection and randomisation	D3.1 Data set of study population with low selection bias
T3.2 Report on new knowledge on reduction of severe irAEs caused by systemic anticancer treatment with ePRO follow-up	D3.2 Report on new knowledge on reduction of severe irAEs caused by systemic anticancer treatment with ePRO follow-up
T3.3 Analysing difference in survival	D3.3 Report on new knowledge on overall survival with ePRO
T3.4 Analysing HRQoL in ePRO patients related to irAE, progression of disease and death.	D3.4 Report on new knowledge on HRQoL in the ePRO study group
T3.5 Write article about findings	T3.5 Published article

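### The HRQoL part of H3 and O3 cannot be tested: QLQ-C30 is collected in the ePRO module, and no HRQoL source is described for the standard follow-up cohort.

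*Protocol*

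**What the plan says.** **The promise.** H3 (section 3.2) predicts: "By implementing ePRO as standard follow-up for cancer patients we predict that we can increase HRQoL and overall survival". Objective O3 (section 3.1) is to introduce ePRO follow-up and "investigate Health Related QoL (HRQoL) and overall survival compared to standard of care". Section 4.1 says the study will look at how ePRO follow-up influences survival and QoL. The WP3 title in section 4.2 likewise names an influence of ePRO on both, and WP3 is said to be based on H3 and to aim at O3.

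**The plan.** The WP3 table in section 4.2 gives the measurement: "HRQoL will be measured using EORTC QLQ-C30 version 3.0(18,19) included in the ePRO module". The introduction describes how the Kaiku Health software delivers it: "Based on received treatment each patient gets a personalised follow-up symptom- and QoL-questionnaire". The comparator in WP3 is a retrospective cohort of 600, including "patients from UNN and HSYK with standard follow-up who received immunotherapy during the years 2020-2023, and matched on cancer diagnosis". On data source, section 4.2 says: "Patient data will be collected from the hospitals shared EHR". Task T3.4 reads: "Analysing HRQoL in ePRO patients related to irAE, progression of disease and death". Its deliverable, D3.4, is likewise a report on the ePRO group.

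**Methods named.** The only between-group method given for WP3, in sections 4.2 and 4.4, is Kaplan-Meier estimation of overall survival.

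**The concern.** H3 makes ePRO follow-up the cause of a gain in HRQoL. Supporting that needs HRQoL scores from patients treated in a similar way but without ePRO. If scores exist only among ePRO users, the available evidence is the course of HRQoL in one group. That course also moves with response to immunotherapy, with regression to the mean, and with the loss of patients who die or stop reporting. A rise or a stable level could not be credited to ePRO, and a fall could not be held against it.

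An SAP cannot repair this, because the gap lies in data collection. QLQ-C30 is self-reported and the comparator's treatment years are 2020-2023. On-treatment scores that were not recorded then cannot be obtained later or rebuilt by record review.

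The provisional title of the WP3 paper (section 7) asks what difference ePRO follow-up makes for patients, which invites an HRQoL claim. Section 10 says WP2 and WP3 will be registered once ethics approval is given, so the wording may enter a public record.

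**Working it through.** **1. The plan's own figure.** There is no HRQoL sample size, effect size or standard deviation to reproduce. The only sizing for WP2-3 (section 4.3) concerns severe adverse events: a 40% reduction, 2:1 allocation, alpha 0.05, 80% power, giving about 300 ePRO and 600 standard care patients. Assume that the 16.6% quoted for WP1 carries over and that the test is two-sided.

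- ePRO rate: 0.166 × 0.6 = 0.0996
- Arcsine effect size: h = 2·asin(√0.166) − 2·asin(√0.0996) = 0.197
- n(ePRO) = (1.960 + 0.842)² × 1.5 / h² ≈ 303, with 606 on standard care

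The stated 300 and 600 are reproduced closely, but they do not bear on HRQoL.

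**2. Outcomes set against data source and analysis.**

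| | Overall survival | HRQoL |
|---|---|---|
| Promised in H3 | increase | increase |
| Promised in O3 | compared with standard care | compared with standard care, on one reading |
| Source, ePRO cohort | hospital EHR | QLQ-C30 in the ePRO module |
| Source, standard follow-up cohort | hospital EHR | none described |
| Task | T3.3, difference in survival | T3.4, ePRO patients only |
| Between-group method | Kaplan-Meier | none named |

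The survival column is complete. The HRQoL column lacks the comparator's data, a between-group task and a between-group method.

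**3. What follows for estimation.** For a difference in mean score, the standard error is SD × √(1/n₁ + 1/n₂), where n₁ and n₂ are the patients with scores in each cohort. If the standard follow-up cohort has none, n₂ = 0 and the expression is undefined, however large n₁ is.

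**4. Patient numbers are not the obstacle.** For illustration only, assume a standard deviation of 20 to 25 points and a difference of 5 points (neither is in the protocol), and suppose that all 300 and 600 patients had a score. Since √(1/300 + 1/600) = 0.0707:

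- SD 25: standard error 1.77, power about 81%
- SD 20: standard error 1.41, power about 94%

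What is missing is a source of scores.

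**5. The protocol's two accounts of WP3.** The introduction says WP3 follows how QoL develops under ePRO follow-up and, separately, compares survival between the two forms of follow-up. T3.4 and D3.4 agree with that. H3, section 4.1 and the WP3 title speak of an effect of ePRO on QoL. The two accounts cannot both describe WP3.

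**The case against.** The strongest reply is that the operational plan is already the right one. The introduction, T3.4, D3.4 and section 4.4 treat HRQoL descriptively and reserve the group comparison for survival. No task or analysis plans a between-group HRQoL test, and section 4.3 calls WP2-3 a pilot. On this view only some ambitious wording is out of line. That is fair as far as it goes, and it is why the remedy is rewording. But H3 is the stated basis of WP3, and a pilot label does not make a causal prediction answerable.

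Second, the comparison in O3 may attach to overall survival alone. The sentence allows that reading, and the task list supports it. The point does not depend on O3, because H3 attributes an HRQoL increase to ePRO by itself.

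Third, change from baseline might be offered as a test of H3. It would describe a course without attributing it to ePRO, and the protocol does not state that a pre-treatment score is collected.

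Two stronger readings are tempting but unsupported. A reader might infer that H3 as a whole is untestable; it is not, since survival has a comparator and a named method. A reader might also infer that none of the 600 comparator patients has an HRQoL score. The protocol does not say so. It only describes no source, and T3.4 makes absence likely.

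**Conclusion.** The point holds for the HRQoL part of H3, and for O3 where O3 is read as comparing HRQoL with standard care. The protocol predicts an effect of ePRO on HRQoL and describes HRQoL data for ePRO patients only. As written, no between-group HRQoL effect can be estimated, and the one-group course cannot support the prediction. The size is structural: HRQoL scores are described for 0 of the 600 comparator patients, which is a statement about the plan's text and not a count of the records.

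The conclusion assumes that standard follow-up means follow-up without the Kaiku module, and that no HRQoL source is named in the figures or other material not available here. The wording should be settled before WP3 is reported, because it decides what the study may conclude.

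**What to change.** Reword four places to agree with the introduction and with T3.4 and D3.4: H3 (section 3.2), O3 (section 3.1), the sentence on influence in section 4.1, and the WP3 title in section 4.2. The revised text should say that:

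- only overall survival is compared with standard care;
- HRQoL is a descriptive aim in the ePRO cohort, covering its course and its association with irAEs, disease progression and death;
- no effect of ePRO on HRQoL will be concluded.

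Alternatively, if the standard follow-up cohort has an existing HRQoL source, name it and keep the comparison.

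The longitudinal model can be left to the SAP. Any analysis of change from a pre-treatment score would first need confirmation that such a score is collected.

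The cost of rewording is one claim given up. Sample size, data collection and the survival analysis stay as they are.

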4.1 Theoretical approach

Development of the NCAF is based on the GTT methodology created by Institute of Healthcare Improvement in 2006 (2). The modified NCAF uses ML technology with algorithms for indexed variables or free text, that will be further developed in this study (8). During the last years, a few different studies have validated cancer-specific triggers by manual review of patient records, identifying AEs related to cancer care (9-12). The ePRO software Kaiku Health is standard of care for cancer patients at the Department of Oncology at NLSH from 2021, using ML to interpret potential irAEs, and QoL by using the EORTC QLQ-C30 version 3.0 providing a QoL-score (19). QLQ is an integrated system for assessing the health-related QoL of cancer patients. In this study we will combine research with ML learning technology to create a fully automated identification of irAEs (WP1), investigate irAEs with NCAF Oncology in clinical practice under ePRO-follow up versus standard follow-up (WP2), and finally how ePRO follow-up influence overall survival and QoL (WP3).

4.2 Study design and methodology

A retrospective quantitative approach will be used to develop and validate new technology and methods since there is a need to control and check the outcomes, before we use an ambi-directional cohort study design to see how the new technology and methods perform in clinical practice on real

world data (20). The study is a multicentre study carried out at the Department of Oncology at NLSH in collaboration with The University Hospital of North Norway (UNN) and Helgeland Hospital Trust (HSYK).

The main inclusion criteria are above 18 years of age, cancer diagnosis as primary or secondary diagnosis according to the ICD-10 classification and receiving immunotherapy as systemic anticancer treatment reported with ATC codes for medications. Patient data will be collected from the hospitals shared EHR. Extracted information from patient records will be anonymised and stored within an encrypted environment at NLSH with restricted access only to certified study personnel, and kept for ten years. No data will be transferred outside the EEA.

The project is operationalised into three work packages (WPs) where cancer patients from all three hospital trusts will be included in one large cohort in WP1. In WP2 and 3 a prospective cohort will be compared to a retrospective cohort from WP1. Figure 2 under is an overview of the three WPs.

[figure not shown]

Figure 2: Overview of the three WPs

The specific methods, tasks (T), description of activities and the outcome deliverables (D) used for each WP are divided and specified in the tables below.

WP1: Automated identification of irAEs in cancer care
Target: WP1 is based on H1, with the aim to reach O1.
Method: Multicentre retrospective cohort study
Description of activities: 600 cancer patients treated with immunotherapy from 2021-2022 will be included and prepared for analytics in a separate technological environment. The use of corticosteroids, Infliximab or

